12.6 Unscheduled Visits

Unscheduled visits may be necessary due to AEs or other reasons. The Investigator may examine a subject as often as is medically necessary while the subject is enrolled in the study. In addition, if the Investigator believes follow-up is needed after the Study Exit or Early Termination visit, it should occur as an unscheduled visit at his/her discretion. Assessments performed at unscheduled visits are at the discretion of the Investigator.

13 Study Assessments

This section describes the study assessment procedures. For timing of study assessments, see the Schedule of Events ([Appendix A](#)). For full details on each study assessment, refer to the Study Manual.

13.1 Informed Consent

At Visit 1 (Screening, within 30 days prior to Baseline [Day 1]), obtain a signed ICF from each subject prior to performing any study related procedures (including any pre-treatment procedures or withdrawal from exclusionary medications). Informed consent must be obtained and documented in the subject's chart prior to initiation of any procedures that are performed solely for the purpose of determining eligibility for research.

13.2 Eligibility Assessment

At Visit 1 (Screening [Day -30 to Day -1], within 30 days prior to Baseline [Day 1]), each inclusion and exclusion criterion must be checked for each subject, as well as restricted and prohibited prior and concomitant therapy. At Baseline (Visit 2/Day 1), eligibility requirements must be reviewed to determine if the subject is still eligible to continue in the study.

13.3 Demographic Data

Demographic data, including age, gender, race, ethnicity, and iris color, will be collected at the screening visit.

13.4 Medical, Surgical, and Ocular History

A medical, surgical, and ocular history should be obtained from each subject at Screening (Day -30 to Day -1) and updated at Baseline (Day 1), and any time the Investigator learns of information that should be included in the subject's medical, surgical, or ocular history.

13.5 Prior and Concomitant Therapy

All current therapies and relevant prior therapies (see Section [11.5](#)) will be assessed at Baseline (Visit 2/Day 1). Concomitant therapies will be collected and recorded throughout the study.

13.6 Pregnancy Testing

A serum pregnancy test will be conducted at the Screening visit (Day -30 to Day -1) and a urine pregnancy test will be conducted at Baseline (Visit 2/Day 1), Visit 6/Day 29 (± 1 day), Visit 7/Day 57 (± 5 days), and Visit 8/Day 85 (± 5 days; Study Exit) for women of childbearing potential.

13.7 Abbreviated Physical Examinations

Abbreviated physical examination, including a review of body systems and height and weight, will be performed by qualified study personnel. Height will only be recorded at the Screening Visit. Abnormal findings will be recorded.

13.8 Vital Signs

Vital signs (systolic and diastolic blood pressure, pulse, and respiratory rate) will be assessed by qualified study personnel after the subject has been resting in a sitting position for at least 5 minutes.

13.9 12-Lead Electrocardiogram

Safety 12-lead ECGs will be obtained by qualified study personnel with the subject in a supine position after resting for at least 3 minutes. ECGs will be read by the Investigator or other qualified designee.

13.10 Clinical Laboratory Evaluations

The laboratory assessments listed in (Table 1) are to be performed according to the Schedule of Events ([Appendix A](#)).

The investigator must review the laboratory results, document this review, and record any clinically significant changes occurring during the study on the AE CRF. All laboratory results must be reviewed prior to the next study visit to evaluate the subject's safety for continued treatment. With the exception of the urine pregnancy test and urinalysis, all laboratory assessments will be performed by a central laboratory.

Table 1 Clinical Laboratory Assessments Performed During the Study

Category	Parameters
Chemistry (serum)	Sodium, potassium, chloride, glucose, blood urea nitrogen, creatinine, calcium, phosphorus, total protein, albumin, ALT, AST, total bilirubin, alkaline phosphatase, creatine phosphokinase, cholesterol, and triglycerides, uric acid, and estimated glomerular filtration rate (eGFR, by the Modification of Diet in Renal Disease Study equation)
Hematology	Hematocrit, hemoglobin, red blood cell count, platelet count, white blood cell count with automated differential (% and absolute count), and HbA1c
Urinalysis	Routine urinalysis (ie, dipstick) without microscopic examination
Coagulation	Prothrombin time (PT), international normalized ratio (INR), fibrinogen, and activated partial thromboplastin time (aPTT)
Pregnancy ^a (serum at Screening, urine at each monthly visit ^b)	β-human chorionic gonadotropin

^a Women of childbearing potential only

^b Urine pregnancy testing will be conducted at Visit 2, Visit 6, Visit 7, Visit 8, and Visit 9 (Study Exit).

13.11 Aqueous Humor Collection for Biomarkers

A 50 µl sample of aqueous humor will be collected from the study eye by paracentesis and shipped the same day on dry ice.

13.12 Visual Acuity

Best-corrected visual acuity (BCVA) will be measured using the ETDRS retro-illuminated chart, the ETDRS electronic visual acuity (ETDRS-EVA) system, or the standard ETDRS wall chart in normal luminance lighting (NL-BCVA). NL-BCVA will be recorded as total letter score in each eye.

Low luminance BCVA (LL-BCVA) will be measured after BCVA is measured in normal luminance. A 2.0 log unit neutral density filter (ie, a filter that lowers luminance by 100 times, such as a Kodak Wratten filter, Rochester, NY), provided by the Sponsor, will be placed over the best correction for each eye in order to perform LL-BCVA.

Visual acuity testing should precede any examination requiring contact with the eye. In order to provide standardization and well-controlled assessments of BCVA during the study, all BCVA assessments at a single site must be consistently done using the same lighting conditions during the entire study. The Investigator should also consistently use the same correction, chart type, and measurement procedure for an individual subject during the entire study.

Detailed instructions for obtaining BCVA will be provided in a study-specific BCVA protocol.

13.13 Slit-lamp Biomicroscopy

Slit-lamp biomicroscopy will be performed prior to dilating the pupil. Magnification will be consistent with standard clinical practice. The subject will be seated during the examination. This procedure should be conducted in the same manner for all subjects and will include an assessment of each of the following as normal or abnormal:

- Eyelids
- Conjunctiva
- Cornea
- Anterior chamber
- Iris
- Lens

All abnormal findings will be described.

13.14 Intraocular Pressure

IOP will be measured in each eye and results will be recorded in mm Hg.

At visits where IOP is to be measured, a single measurement will be made. Contact or non-contact tonometry can be performed. The same tonometry method should be used throughout the study.

The tonometer must be calibrated for accuracy before the first subject in the study undergoes the first examination and according to manufacturer specifications during the study, until the last subject has exited the study.

13.15 Gonioscopy

The anterior chamber angle will be assessed for degree of openness and NV with gonioscopy at Visits 1, 2, and 8. Gonioscopy may be performed at any other visit, based on the Investigator's clinical judgement.

13.16 Dilated Ophthalmoscopy

A dilated fundus examination will be performed for each eye in all subjects. The following will be observed for the presence of abnormalities:

- Vitreous
- Peripheral retina
- Macula
- Choroid
- Optic nerve

All abnormal findings will be described.

13.17 Color Fundus Photography

Color fundus photographs (both eyes, 9 fields) will be performed to assess lesion characteristics of each eye for all subjects. Photographs will be transmitted to and evaluated by the central reading center.

Color fundus photographs will be obtained using a fundus camera which has been certified by the central reading center. The study personnel who perform fundus photography will be trained and certified by the central reading center prior to enrollment of subjects.

Detailed instructions for imaging and image transfer will be provided in the study-specific Image Acquisition and Submission Protocol.

13.18 Spectral Domain Optical Coherence Tomography

SD-OCT will be performed to assess lesion characteristics and retinal structure of each eye for all subjects. For SD-OCT, Heidelberg Spectralis models must be used. Images will be evaluated by the Investigator. The images will also be transmitted to and evaluated by the central reading center.

The study personnel who perform SD-OCT will be trained and certified by the central reading center prior to enrollment of subjects.

Detailed instructions for imaging and image transfer will be provided in the study-specific Image Acquisition and Submission Protocol

13.19 Fluorescein Angiography

Fluorescein angiography (FA; both eyes, 9 fields) will be performed to examine the circulation of the retina on each eye for all subjects. Images will be evaluated by the Investigator. Images will also be transmitted to the central reading center.

The study personnel who perform FA will be trained and certified by the central reading center prior to enrollment of subjects.

Detailed instructions for imaging and image transfer will be provided in the study-specific Image Acquisition and Submission Protocol

13.20 Retinal Oximetry Imaging

Non-invasive retinal oximetry imaging may be performed at selected sites. If obtained, images will be transmitted to and evaluated by the central reading center.

The study personnel who perform retinal oximetry imaging will be trained and certified by the central reading center prior to enrollment of subjects.

13.21 Evaluation of Adverse Events

All AEs (serious and nonserious) must be recorded in the source documents and AE eCRFs, regardless of causal relationship with study drug or procedures. AEs must be captured from the time the subject signs the ICF through the earlier of either the final study visit or 30 days after the last study drug dose. The following information will be collected about each AE: severity, onset and resolution dates and times, frequency, seriousness, relationship to study drug, action taken, outcome, location, and whether the AE caused the subject to discontinue from the study.

13.21.1 Definitions

An **adverse event** is any untoward medical occurrence in a subject administered a study drug and does not necessarily have to have a causal relationship with the study drug.

AEs may include:

- Any unfavorable sign, medical diagnosis, or symptom. Whenever possible, the Investigator should group signs or symptoms that constitute a single diagnosis under a single AE term (eg, “cough, rhinitis, and sneezing” might be grouped together as “upper respiratory tract infection”).

- An unfavorable change of a pre-existing condition that occurs during the protocol-defined reporting period.
- Clinically significant laboratory abnormalities, ophthalmic assessments, or vital signs. If possible, abnormal laboratory results or changes in vital signs that meet the definition of an AE should be reported as a clinical diagnosis, rather than the abnormal laboratory value (eg, “hypertension” rather than “blood pressure increased”).

Special considerations include:

- A medical or surgical procedure, itself, should not be captured as an AE. The Investigator should determine whether or not the medical condition or diagnosis necessitating such treatment is an AE, eg, the worsening of a pre-existing condition or a new diagnosis.
- Changes in pre-existing medical conditions, including worsening severity, frequency, or character during the protocol-defined reporting period, should be recorded as AEs.
- Death itself is not considered an AE. The cause of death should be reported as an SAE.
- Pregnancy is not an AE. Pregnancy in a female subject or the partner of a male subject should be reported to the Sponsor in accordance with Section [13.21.4](#).

A **treatment-emergent AE** is any AE that occurs after the subject has received the first dose of study drug, whether or not it is considered causally related to the study drug.

A **Serious Adverse Event** includes any event that, in the view of either the Investigator or Sponsor, results in any of the following outcomes:

- Death.
- Life-threatening (ie, the subject was at immediate risk of death at the time of the event). It does not refer to an event that hypothetically might have caused death if it were more severe.
- Requires inpatient hospitalization or prolongation of existing hospitalization. Hospitalization for surgery planned before study entry is not considered an SAE.
- A persistent or significant incapacity or substantial disruption of the ability to conduct normal life functions.
- A congenital anomaly/birth defect of offspring.
- An important medical event that might not be immediately life-threatening or result in death or hospitalization, but might jeopardize the subject or might require intervention

to prevent one of the outcomes listed in the definition above. Examples of such events are intensive treatment in an emergency room or at home for allergic bronchospasm, blood dyscrasias or convulsions that do not result in inpatient hospitalization, or the development of drug dependency or drug abuse.

AE Severity:

AEs will be graded using National Cancer Institute Common Terminology Criteria for Adverse Events (CTCAE) v 4.03. The criteria can be accessed at:

http://evs.nci.nih.gov/ftp1/CTCAE/CTCAE_4.03_2010-06-14_QuickReference_8.5x11.pdf.

The term “severe” is a measure of intensity. A severe AE is not necessarily a serious AE.

Study Drug Causality: Relationship of an AE to treatment will be assessed by the investigator as follows:

Causality	Definition
Related	There is a reasonable causal association with administration of the drug; the event is confirmed by stopping and/or restarting the drug or is not explained by any other reasonable hypothesis; there is evidence to suggest a causal relationship between the drug and the AE.
Not related	There is no causal or temporal relationship to the study drug administration; related to other etiologies such as concomitant medications or conditions.

13.21.2 Adverse Event Reporting Procedures

Subjects will be instructed to report all AEs that occur during their study participation. The Investigator will assess subjects for the occurrence of AEs at all scheduled and unscheduled visits. The occurrence of AEs should be elicited by non-direct questioning of the subject at each visit, eg, “Have you had any problems since your last visit?” The Investigator may detect AEs while performing a physical examination or other assessments. All AEs (serious and nonserious) reported by the subject will be reviewed by a qualified Investigator in the study and must be recorded on the source documents and AE eCRFs.

An AE that is serious must be reported on an SAE form to the Sponsor’s Drug Safety department no later than 24 hours after the Investigator becomes aware of the event.

[REDACTED]

All SAEs occurring after the ICF is signed but before administration of study drug that are considered **related** to a protocol procedure must also be reported to Drug Safety within 24 hours after the clinical site becomes aware of the event.

For SAEs that occur before the first dose of study drug is administered and that are considered **unrelated** to any study procedure by the Investigator, record the SAE on the AE eCRF only; completion of an SAE form and reporting to Drug Safety is not required for such events.

If an ongoing SAE changes in intensity, outcome, or the relationship to study drug, a follow-up SAE report should be sent to the Sponsor within 24 hours after the clinical site becomes aware of the change in status.

13.21.3 Reporting Serious Adverse Events to Regulatory Agencies

The Sponsor will determine which SAEs qualify for expedited reporting. Reports of those SAEs that qualify for expedited reporting will be submitted to regulatory agencies in accordance with applicable local regulation (eg, 21 Code of Federal Regulations [CFR] 312.32). Expedited reports will be also distributed to Investigators and will be submitted to the IRB in accordance with institutional guidelines and local regulation.

13.21.4 Pregnancy

Pregnancy itself is not an AE. However, any report of pregnancy that occurs in a female subject or the female partner of a male subject during study participation or within 90 days after the subject's last dose of study drug, and that becomes known to the Investigator, must be reported to the Sponsor even if the subject is withdrawn from study.

If a subject or Investigator suspects that a subject may be pregnant prior to study drug administration, the study drug administration must be withheld until the results of blood serum or urine pregnancy tests are available. If pregnancy is confirmed, the subject must not receive the study drug and must not be enrolled in the study. If pregnancy is suspected while the subject is receiving study treatment, the study drug must be withheld immediately until the result of the serum pregnancy test is known. If pregnancy is confirmed, the study drug will be permanently discontinued and the subject will be withdrawn from the trial.

The Investigator must follow the pregnancy to conclusion and will collect data on both maternal and fetal outcome including follow-up information regarding the course of the pregnancy, including perinatal and neonatal outcome. Normal outcomes will be communicated to the Sponsor within 30 calendar days of birth/delivery. Infants will be followed for a minimum of 6 months.

All abnormal pregnancy outcomes and/or any AE for the child or fetus (including miscarriage) will be recorded on the AE eCRF and SAE form. The associated SAE form will be sent to and followed up by the Sponsor according to the procedure described in Section 13.21.2.

An AE eCRF and/or SAE form, as appropriate, will be completed for subjects who are maternal to the child or fetus and if the subject sustains an AE. The SAE form will be sent to the Sponsor in accordance with Section 13.21.2.

13.21.5 Overdose

Overdose is defined as any dose higher than the defined or prescribed dose of study drug. Occurrences of overdose leading to AEs will be reported on the AE eCRF.

An overdose leading to an SAE will be reported to the Sponsor in accordance with the procedure described in Section 13.21.2.

13.21.6 Follow-up of Adverse Events

Subjects with ongoing SAEs will be followed until the event(s) is resolved, stabilized, no longer considered clinically significant by the Investigator, or the subject dies or withdraws consent.

Resolution means the subject has returned to the baseline state of health. Stabilization means the Investigator does not expect any further improvement or worsening in the subject's condition.

All nonserious AEs will be followed through the last scheduled or unscheduled visit.

For a nonserious AE that is first identified on the last scheduled contact (and with onset ≤ 30 days after the last study drug dose), the event must be recorded on the AE eCRF with the current status noted, but no further follow-up needs to be performed.

13.21.7 Follow-up of Post-study Serious Adverse Events

Any new SAE reported by the subject to the Investigator, with onset after the earlier of the final study visit or 30 days after the last study drug dose and that is determined by the Investigator to be associated with the use of study drug, should be reported to the Sponsor.

The Investigator should follow these related SAEs and continue to report any significant follow-up information to the Sponsor until the events are resolved or stabilized, or the subject is lost to follow-up.

14 Data Monitoring Committee

No involvement of an Independent Data Monitoring Committee is planned. A Safety Review Team consisting of Sponsor staff and/or consultants will periodically review masked safety data.

15 Study Endpoints

15.1 Primary Efficacy Endpoint

The primary study endpoints are the change in aqueous humor concentration of eight biomarkers (IL-6, IL-8, IP-10, PDGF-AA, TGF β -1, MCP-1 and IL-1 β , and VEGF) from baseline (Day 1) to Day 85, the conclusion of an 84-day course of study drug. Analysis will include both absolute change and percent change from Baseline (Visit 2/Day 1) to Day 85 (Visit 8/Study Exit).

15.2 Secondary Efficacy Endpoints

The secondary efficacy endpoints will include:

1. Change in area of retinal NV from baseline to Day 85, as assessed by the central reading center from color fundus photographs
2. Change in degree of vitreous hemorrhage from baseline to Day 85, as assessed by the central reading center from color fundus photographs
3. Change in degree of preretinal hemorrhage from baseline to Day 85, as assessed by the central reading center from color fundus photographs
4. Change in NL-BCVA from baseline to Day 85
5. Change in CST from baseline to Day 85, as assessed by the central reading center from SD-OCT, in subjects with DME
6. Change in retinal vessel oxygen saturation from baseline to Day 85, as assessed by the central reading center from retinal oximetry imaging

16 Statistical Analysis and Study Variables

Eight subjects per arm yields 80% power to detect a difference between emixustat and placebo in each aqueous humor biomarker, assuming an effect size of 1.31, using a two-sample t-test and a two-sided alpha level of 0.10. To account for potential early termination subjects, 2 additional subjects per treatment arm, for a total of 10 subjects per arm, will be enrolled.

Subject demographic and baseline data will be summarized by treatment arm for all randomized subjects. Continuous variables will be summarized using descriptive statistics (number of subjects, mean, standard deviation (SD), median, minimum and maximum), and categorical variables will be summarized using the count and percentage of subjects in each category.

Primary and secondary endpoints will be summarized using standard quantitative (sample size, mean, SD, median, minimum, maximum, and 90% and 95% t-distribution confidence intervals [CI] around the mean) and qualitative (frequency counts, percentages, and exact 90% and 95% CIs around the percentages) summary statistics and assessed using two-sided 90% and 95% t-distribution CIs and two-sided, two-sample t-tests around the differences between treatment groups for quantitative measures. For the assessment of changes from baseline in aqueous humor concentration of the 8 biomarkers, both absolute and percent changes will be analyzed. Additionally for quantitative measures, 1-sample t-tests will be completed on the change from baseline values within a treatment group. Qualitative measures will be analyzed by exact McNemar's test for changes within a treatment group and Fisher's Exact Test for differences between treatment groups. Differences in proportions and 90% and 95% CIs will also be presented for comparisons between treatment groups for qualitative variables.

The assessment of safety will be based on the summaries of ocular and non-ocular AEs, NL-BCVA, LL-BCVA, ophthalmic examination findings (slit lamp biomicroscopy, dilated ophthalmoscopy, IOP, gonioscopy), SD-OCT, vital signs, physical examination findings, ECGs, and clinical laboratory values. Subjects will be summarized in the group according to the treatment received, and all subjects receiving emixustat will be combined into one group.

AEs reported during the study will have their verbatim terms mapped to the corresponding thesaurus terms from the most current version of the Medical Dictionary for Regulatory Activities (MedDRA[®]) coding dictionary. All summaries of AEs will be based on the assigned MedDRA Preferred Term and System Organ Class, and summaries will be given for each of the two randomized treatment arms.

Separate summaries of AEs related to treatment (as reported by the Investigator) and by severity will be prepared. The number of SAEs will also be presented, and events leading to discontinuation from the study will be listed and tabulated.

17 Data Handling and Quality Assurance

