9.2 Inclusion Criteria

Subjects who meet all of the following criteria at screening and baseline (unless otherwise indicated) may be eligible for inclusion in the study:

1. Able and willing to provide a written informed consent before undergoing any study-related procedures.
2. In the opinion of the investigator, the ability and willingness to return for all scheduled visits and perform all assessments.
3. Males or females, ≥ 18 and ≤ 85 years of age at the Screening Visit.
4. A documented diagnosis of type 1 or type 2 diabetes mellitus. Any one of the following will be sufficient evidence that diabetes is present:
 - a. Current regular use of insulin for the treatment of diabetes
 - b. Current regular use of an oral anti-hyperglycemia agent for the treatment of diabetes
 - c. Documented diabetes by American Diabetes Association and/or World Health Organization (WHO) criteria (see [Appendix C](#) for definitions)
5. The following ocular criteria for the study eye:
 - a. Presence of PDR with or without DME for which, in the Investigator's judgment, interventional treatment can be safely deferred for at least 4 weeks after the Day 1 visit.
 - b. No prior pan-retinal photocoagulation (PRP); defined as ≥ 500 burns placed previously outside the posterior pole.
 - c. No intravitreal injection of an anti-VEGF agent in the 3 months prior to randomization (Day 1).
 - d. No intravitreal or peri-bulbar injection of a corticosteroid in the 4 months prior to randomization (Day 1).

- e. Early Treatment Diabetic Retinopathy Study (ETDRS) NL-BCVA letter score of ≥ 24 (approximate Snellen equivalent 20/320) on the day of randomization (Day 1).
- f. Media clarity, pupillary dilation, and subject cooperation sufficient to obtain adequate fundus photographs and SD-OCT.

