11. Any of the following laboratory abnormalities at screening:
- a. Aspartate transaminase (AST)/alanine transaminase (ALT) >3.0 x upper limit of normal (ULN)
 - b. Total bilirubin >1.5 x ULN
 - c. Estimated glomerular filtration rate (eGFR) < 60 mL/min/1.73 m²
 - d. Impaired coagulation: International Normalized Ratio (INR), prothrombin time (PT), or activated partial thromboplastin time (aPTT) >1.25 x ULN.
 - e. Impaired hematologic function: hemoglobin <9.0 g/dL; neutrophil count $<1.6 \times 10^9$ /L; or platelet count $<100 \times 10^9$ /L
 - f. Any laboratory screening test that meets the abnormality criteria stated above can be repeated once within the period from screening to baseline.
12. Any of the following ocular characteristics in the study eye:
- a. Tractional retinal detachment involving the macula. A tractional retinal detachment is not an exclusion if it is outside the posterior pole (not threatening the macula) and, in the Investigator's opinion, is not considered a contraindication to deferring PRP, anti-VEGF therapy, or surgical intervention.
 - b. Exam evidence of NV of the angle (NV of the iris alone is not an exclusion if it does not preclude deferring PRP or anti-VEGF therapy)
 - c. A decrease in BCVA due to causes other than diabetic retinopathy (eg, foveal atrophy, pigment abnormalities, dense sub-foveal hard exudates, previous vitreoretinal surgery, non-retinal condition, substantial cataract, or macular ischemia) in the Investigator's opinion.

- d. An ocular condition (other than diabetic retinopathy) that, in the opinion of the Investigator, might alter visual acuity during the course of the study (eg, retinal vein or artery occlusion, uveitis or other ocular inflammatory disease, neovascular glaucoma, etc.). A vitreous or preretinal hemorrhage is not an exclusion if it is out of the visual axis and, in the Investigator's judgement, is not having any effect on visual acuity.
 - e. History of major ocular surgery (including vitrectomy, cataract extraction, scleral buckle, any intraocular surgery, etc.) within 3 months prior to the Screening Visit or anticipated to occur within during the course of the study.
 - f. History of YAG capsulotomy performed within 2 months prior to randomization (Day 1) or anticipated during the course of the study.
 - g. Aphakia
 - h. Uncontrolled glaucoma (in the Investigator's judgement).
 - i. Exam evidence of periocular or ocular infection (eg, blepharitis, chalazion, or conjunctivitis).

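### Does section 16 need to say whether degree of haemorrhage is tested as a quantitative or a qualitative measure?

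*Combined protocol and SAP*

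**What the plan says.** Section 15.2 lists, as secondary endpoints 2 and 3, "Change in degree of vitreous hemorrhage from baseline to Day 85, as assessed by the central reading center from color fundus photographs" and "Change in degree of preretinal hemorrhage from baseline to Day 85", the second also read centrally from color fundus photographs. Neither there nor in the synopsis, section 8.5 or section 13.17 is there a scale, a number of grades or a variable type.

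Section 16 sorts the tests by type of measure. Quantitative measures get two-sample t-tests between arms, and "Additionally for quantitative measures, 1-sample t-tests will be completed on the change from baseline values within a treatment group". For the other type, "Qualitative measures will be analyzed by exact McNemar's test for changes within a treatment group", with Fisher's exact test between arms; in addition, "Differences in proportions and 90% and 95% CIs will also be presented for comparisons between treatment groups for qualitative variables". Counts and percentages are also planned for qualitative endpoints. Apart from the biomarkers, no endpoint is named under either type.

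Section 13 opens with a pointer elsewhere: "For full details on each study assessment, refer to the Study Manual". Two eligibility rules bear on how much haemorrhage can be present at entry. Section 9.2 requires "Media clarity, pupillary dilation, and subject cooperation sufficient to obtain adequate fundus photographs and SD-OCT". Section 9.3 states that "A vitreous or preretinal hemorrhage is not an exclusion if it is out of the visual axis", provided the investigator judges that it does not affect acuity.

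**The concern.** The biomarkers, neovascular area, visual acuity, central subfield thickness and oxygen saturation are all numeric. The two haemorrhage endpoints are therefore the only listed efficacy endpoints for which the qualitative methods look written, and a reader could reasonably put them there.

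If the scale has several ordered grades, those methods fit badly. McNemar's test and a difference in proportions need a yes/no variable, so someone must choose a cut. A cut at presence versus absence would count movement between two non-zero grades as no change, and eyes may enter with haemorrhage. Fisher's test on the full table keeps the grades but ignores their order. At stake would be some sensitivity to worsening or improvement on two secondary endpoints, and the freedom to choose a cut-point late.

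**Working it through.** **The plan's own figure.** Inputs from section 16: 8 per arm, effect size 1.31, two-sample t-test, two-sided alpha 0.10. With df = 2 × 8 − 2 = 14 and noncentrality 1.31 × √(8/2) = 2.62, power is 80.1%, which agrees with the stated 80%. That figure is for the biomarkers. Nothing comparable is given for haemorrhage, and section 16 sets no significance level for secondary endpoints. The 0.10 level is borrowed below.

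**How coarse the qualitative tests are at this size.**
- Exact McNemar, all m discordant subjects moving the same way: p = 2 × 0.5^m. For m = 4, p = 0.125; for m = 5, p = 0.0625. Five are needed to reach 0.10.
- Fisher on worsened/not, 0 against 4 events: at 8 per arm p = 2 × C(8,4)/C(16,4) = 2 × 70/1820 = 0.077; at 10 per arm p = 2 × C(10,4)/C(20,4) = 2 × 210/4845 = 0.087. Four against none is the smallest such contrast that reaches 0.10.

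**Does Fisher ignore order?** Yes. A 2 × 4 table with rows (4,3,1,0) and (1,1,2,4) gives p = 0.092. Rearranging its grade columns to (3,0,4,1) and (1,4,1,2) leaves p at 0.092, while the exact rank-sum p moves from 0.019 to 1.0.

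**What that costs.** The documents give no grade distribution, so these are assumptions (probabilities of each change in grade, placebo then drug):
- A, most eyes unchanged (0/+1/+2): .60/.25/.15; .90/.08/.02
- B, about 60% unchanged (−2 to +2): .03/.07/.55/.22/.13; .08/.17/.65/.07/.03
- C, moderate shift (−2 to +2): .05/.15/.35/.30/.15; .15/.30/.35/.15/.05
- D, large shift (−2 to +2): .05/.10/.30/.35/.20; .20/.35/.30/.10/.05

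Power is the summed probability of all pairs of arm outcomes that reject at two-sided 0.10. It is shown in % at 8 / 10 per arm:

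| Case | Fisher, worsened/not | Fisher, full table | Exact rank-sum | t-test on grades |
|---|---|---|---|---|
| A | 19.5 / 29.1 | 21.2 / 31.0 | 22.4 / 34.0 | 40.4 / 48.9 |
| B | 13.7 / 21.2 | 16.1 / 22.0 | 25.8 / 35.1 | 35.4 / 41.6 |
| C | 12.4 / 18.6 | 17.7 / 22.2 | 30.5 / 38.2 | 35.5 / 41.4 |
| D | 30.2 / 43.9 | 36.6 / 46.8 | 57.4 / 68.5 | 61.4 / 69.9 |

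Fisher against rank-sum:
- A: smallest gap 22.4 − 21.2 = 1.2, largest 34.0 − 29.1 = 4.9.
- B: 9.7 to 13.9.
- C and D: from 30.5 − 17.7 = 12.8 to 57.4 − 30.2 = 27.2. These cases need 65% to 70% of eyes to change grade.

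The t-test against rank-sum: from 69.9 − 68.5 = 1.4 to 40.4 − 22.4 = 18.0, always in favour of the t-test.

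**Is the t-test's advantage bought with false positives?** With the same distribution in both arms and 75% unchanged (.75/.165/.085), the t-test rejects 9.5 / 10.2% of the time and the exact rank-sum 3.1 / 4.6%, against a nominal 10%. The t-test stays close to its level; the rank-sum test is conservative because of ties.

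**Within an arm.** Ten illustrative subjects with grades 0,0,0,0,0,1,1,2,2,3 moving to 1,1,0,0,0,2,3,3,3,4:
- McNemar on presence/absence has 2 discordant subjects: p = 2 × 0.5² = 0.50.
- Comparing worsened with improved on the same data, 7 to 0: p = 2 × 0.5⁷ = 0.016, the same as the exact signed-rank test.
- Planned one-sample t-test: mean change 0.8, standard error 0.2, t = 4 on 9 df, p = 0.003.

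The poor McNemar result comes from the presence/absence cut. A discordant-pair test on direction of change does not share it.

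**The case for a change.** The strongest case for a change is that it costs one sentence. A manual that explains how photographs are graded does not choose a statistical test; that choice belongs in section 16, which permits either route. In the table the route matters: t-test minus Fisher runs from 69.9 − 46.8 = 23.1 points (D, full table, 10 per arm) to 61.4 − 30.2 = 31.2 (D, worsened/not, 8 per arm), and in A it is still 48.9 − 31.0 = 17.9 or more. An unstated route and cut-point could be settled after results are seen.

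The textual part stands: neither scale nor route is given. The rest does not establish a defect. The endpoint is worded as a change in degree, which fits a numeric grade and the t-test at least as well as a yes/no variable, and on that route nothing is lost. If the scale has two levels, McNemar and Fisher are usable as written. Replacing the t-test by rank tests would lower power in every case above; that is a preference between acceptable methods. Section 10.2 keeps the sponsor's study staff masked until database lock, and the reading center's scale does not depend on treatment assignment, so the variable type can be settled without knowledge of the results.

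**Conclusion.** No change to the plan is called for. The protocol leaves out a detail, the scale and hence the variable type for two secondary endpoints, which an analyst fills once the reading center's grading form is in hand: numeric or ordered grades go to the planned t-tests on change, a two-level reading to McNemar and Fisher.

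The damage is conditional on more than two grades, a decision to treat them as qualitative, and frequent movement between grades. None of these is documented. The requirement for clear media and the limits on haemorrhage at entry make the case with most eyes unchanged plausible. There Fisher gives up 1 to 5 points against a rank test, and both fall well short of the planned t-test. Gaps of 13 to 27 points appear only if about two thirds of eyes change grade.

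All power figures rest on assumed distributions and a borrowed 0.10 level, so they show direction and rough size only. The primary biomarker analysis and the sample size are untouched, and no decision rule depends on these endpoints.
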